4.2 Analysis Sets

The full analysis set (FAS) is defined as all enrolled subjects. All efficacy and safety analyses will be performed on the FAS.

4.3 Assessment Windows

For the purpose of analyzing time to event endpoints, the time-in-study for each patient will be measured relative to Day 0, the day of transplantation.

For the purpose of listing and summarizing data, the time-in-study for each patient observation will be defined using study days. Such days will be measured relative to Day 0, the day of transplantation.

All data will be summarized by visit based on the visit in which the data was recorded in the database.

Baseline will be defined as the last pre-intervention value during the screening period. If more than one assessment exists within a single visit window, the value closest to the protocol study visit will be used for summary and analysis purposes. Data from all assessments will be listed.

4.4 Handling of Dropouts or Missing Data

The primary safety analysis is the proportion of subjects with a PDG3 at T72. PGD is measured in all lung transplant subjects at specific intervals following transplantation, including 24, 48, and 72 hrs. Protocol training will focus on the importance of obtaining PGD at T72 in every study

subject.

If a subject dies prior to T72 measurement, they will be counted as a “failure” and classified as PGD3 for the primary safety analysis. If the T72 value is missing (not collected, not reported, not properly documented), then PGD3 will be assumed (“failure”), and they will be classified as such for the primary safety analysis. Missing data in other safety analyses will remain missing.

4.5 Multiple Comparisons

No multiple comparisons are planned for this study.

5. STUDY SUBJECTS

5.1 Disposition of Subjects

A table of counts of subjects in the FAS will be provided. Reasons for not completing study as planned and reasons for premature withdrawal will be tabulated for the groups.

5.2 Protocol Deviations

A listing of all protocol deviations will be provided. Distribution for the types of protocol deviations and the number of subjects that deviate from the protocol will be tabulated for the groups.

5.3 Demographic and Baseline Characteristics

Demographic data and baseline characteristics for all FAS subjects collected prior to transplant will be listed and summarized overall, by Transplant Group (EVLP or Control), as well as by transplant subtype (SLT or DLT) using descriptive statistics.

5.3.1 Recipient Demographics and Baseline Characteristics

The following demographic variables for the recipient will be summarized:

- Sex, race/ethnicity, age (years) at time of transplantation
- Weight (kg) and height (cm)
- ABO blood group, “A” blood group subtype, Rh factor
- LAS Disease Diagnosis Group
- Lung Allocation Score at time of waitlist addition and at time of lung match

5.3.2 Donor Demographics and Characteristics

The following demographic variables for the donor will be summarized:

- Sex, race/ethnicity, age (years) at death
- Weight (kg) and height (cm)
- ABO blood group, “A” blood group subtype, Rh factor
- Primary cause, mechanism, and circumstances of death

5.3.3 EVLP Information

- Lungs received (single right, single left, bilateral)
- EVLP time (hours)
- Donor lung evaluation (met transplant inclusion criteria, accepted for transplant)
- Organs shipped

5.3.4 Procurement Information

- Donor type
- Donor and recipient ABO blood group match
- Lung type
- Lung inclusion criteria met
- Ventilation parameters (terminal PaO₂, tidal volume, FiO₂, PEEP, rate)
- Procurement information (Flush solution, flush type, vasodilator, antegrade volume, retrograde volume)

5.4 Medical History

All medical conditions and surgical procedures will be classified by system organ class (SOC) and preferred term (PT) using the Medical Dictionary for Regulatory Activities (MedDRA). The number and percent of subjects with each medical condition and surgical procedure will be presented overall and by transplant subtype for each SOC and PT. The data will also be listed.

5.5 Prior and Concomitant Medications

Concomitant medications will be coded using World Health Organization (WHO) drug classifications. The number and percent of FAS subjects using concomitant medications at each visit will be tabulated by Anatomical, Therapeutic, and Chemical (ATC) class, and by preferred name, transplant subtype and overall.

The use of concomitant medications in the 2 weeks leading up to the onset of a serious adverse event (SAE) will be summarized. The number and percent of FAS subjects using each concomitant medication in that period prior to a SAE will be tabulated by Anatomical, Therapeutic, and Chemical (ATC) class, and by preferred name, transplant subtype and overall.

6. EFFECTIVENESS ANALYSIS

The study endpoints are safety related and therefore there will be no effectiveness analyses.

6.1 Primary Endpoints and Analysis

Primary Graft Dysfunction Score

The PGD3 Score at 72 hours post-transplant (T72) will be used as the basis for the primary safety endpoint for analysis. The primary endpoint (PGD3 T72) will be calculated from PGD T72 as follow: PGD T72 = {0, 1, & 2} will be coded to PGD3 T72 = 0 and PGD T72 = {3} will be coded

to PGD3 T72 = 1.

If a subject dies prior to the T72 measurement, they will be coded to PGD3 T72 = 1. If the T72 value is missing (not collected, not reported, not properly documented), then PGD3 will be coded to PGD3 T72 = 1 for the primary safety analysis.

The subject's PGD Score is to be determined by the Investigator at Baseline (Day 0) after transplantation and upon admission to the ICU, as well as 24, 48, and 72 hours post-transplant.

The primary analysis will be descriptive. The proportion of subjects with PGD3 T72 by Transplant Group (EVLP and Control) will be presented along with a two-sided 95% CI.

There will be no inferential testing conducted.

30-Day Mortality

Subject survival, measured as living or dead, will be recorded for Day 30, Month 6, and Year 1 post-transplant. The primary endpoint of 30-Day mortality will be derived as follows: Living at Day 30 will be coded to 0, and Dead before or on Day 30 will be coded to 1. If the vital status of the subject is missing (not collected, not reported, not properly documented), then 30-Day Mortality will remain missing for the primary analysis.

The primary analysis will be descriptive. The proportion of subjects with 30-Day Mortality by Transplant Group (EVLP and Control) will be presented along with a two-sided 95% CI.

Other supportive endpoints may be provided to supplement the primary analysis, including, but not limited to median number of days to death and primary cause of death.

Results may be displayed graphically. There will be no inferential testing conducted.

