9 PLANNED STATISTICAL METHODS

9.1 General Considerations

This section describes the planned statistical analyses in general terms. A complete description of the methodology will be specified in a statistical analysis plan (SAP), which will be finalized prior to database lock. Any changes in the statistical methods described in this protocol that occur prior to database lock will be documented in the statistical analysis plan and will not require a protocol amendment.

Statistical analysis will be performed primarily on data collected during the Analysis Phase (1-year post-intervention). The database will be locked for analysis of endpoints after the last subject completes his/her study visit at Year 1, and all queries have been resolved. The Long-term Follow-up data will be summarized when the study has completed in support of long-term evaluation.

No statistical hypotheses will be tested in this study. For ease of presentation, contextual review and statistical programming, the descriptive statistics of the contemporaneous Control group will be presented with those of the EVLP group. Descriptive statistics will be presented as means, standard deviations (SD), medians, and ranges for the continuous variables and as frequencies and percentages for categorical variables. Tabulations will be used to summarize results from descriptive summaries and statistical analyses. A one-sided 95.0% CI will be provided, as appropriate, for the primary endpoints, and two sided 95.0% CI will be presented for all endpoints, as appropriate.

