9.5 Primary Endpoint(s)

9.5.1 Primary Graft Dysfunction Grade 3 at 72 hours Post-transplant

The PGD3 Score at 72 hrs post-transplant (T72), as defined in Section 6.7, will be used as the basis for the primary safety endpoint for analysis. The primary endpoint (PGD3 T72) will be calculated from PGD T72 as follows: PGD T72 = {0, 1, & 2} will be coded to PGD3 T72 = 0 and PGD T72 = {3} will be coded to PGD3 T72 = 1.

If a subject dies prior to the T72 measurement, they will be coded to PGD3 T72 = 1. If the T72 value is missing (not collected, not reported, not properly documented), then PGD3 will be coded to PGD3 T72 = 1 for the primary safety analysis.

The primary analysis will be descriptive as the proportion of subjects with PGD3 T72 by Transplant Group (EVLP and Control). A one-sided 95% CI will be calculated around the proportion. A two-sided 95% CI will also be calculated.

There will be no inferential testing conducted.

9.5.2 30-Day Mortality

Subject survival, measured as living or dead, will be recorded for Day 30, Month 6, and Year 1 post-transplant (see Section 6.8). The primary endpoint of 30-Day mortality will be derived as follows: Living at Day 30 will be coded to 0, and Dead before or on Day 30 will be coded to 1. If the vital status of the subject is missing (not collected, not reported, not properly documented), then 30-Day Mortality will remain missing for the primary analysis.

The primary analysis will be descriptive as the proportion of subjects with 30-Day mortality, summarized by Transplant Group. A one-sided 95% CI will be calculated around the proportion. A two-sided 95% CI will also be calculated.

Other supportive endpoints may be provided to supplement the primary analysis, including, but not limited to, median number of days to death and primary cause of death.

Results may be displayed graphically. There will be no inferential testing conducted.

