9. SAMPLE SIZE AND POWER CALCULATIONS

In order to provide a sufficient number of subjects for reliable estimation of the primary endpoints, sample size was calculated based on a primary endpoint of PGD3 at T72. Estimates of PGD3 at T72 were based on historical data from EVLP transplant studies where EVLP subjects had rates of PGD3 at T72 ranging from 0% to 15% and conventional transplant subjects ranging from 16.8% to 30%. Assuming a PGD3 at T72 of 10% and a one-sided 95.0% confidence interval (CI) for a single proportion using the large sample normal approximation adjusted for a finite population of size 2057 (number of lung transplants performed in the US in 2015), 66 subjects will be needed for the expected upper bound of the CI to not exceed a rate of 16%. A total of 66 EVLP subjects and 66 Control subjects will be included in this study.

Rates of 30-day mortality in the EVLP transplant studies have been low, ranging from 3% to 4%. For a sample size of 66, the probability of observing at least one event will be approximately 87% to 93% if the true probability of 30-day mortality is 3% to 4%. Subjects will be entered into the study as EVLP transplants occur; however, enrollment to either transplant subtype (single-lung, double-lung) will be limited to 44 subjects to provide a reasonable number of subjects of both subtypes for subgroup examinations.

A contemporaneous Control group will be entered into this study. This Control group will provide context of the EVLP results and estimation of Control group parameters for design of future studies. All analyses of the Control group will be descriptive and no formal statistical comparison will be made between the EVLP and Control groups. As such, the sample size for the Control group will be 66 subjects, and subjects will be matched to the EVLP Group for similarity. Because the ratio of standard lung transplant to EVLP transplant is estimated to be approximately 4:1, it is feasible to obtain a control-EVLP match within the anticipated duration of the study.

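### Does it matter that SAP 6.1 names no method for the confidence intervals on the two primary proportions?

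*SAP*

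**What the plan says.** SAP 6.1 (Primary Endpoints and Analysis) treats the two primary endpoints alike. For PGD3: "The proportion of subjects with PGD3 T72 by Transplant Group (EVLP and Control) will be presented along with a two-sided 95% CI". For 30-day mortality: "The proportion of subjects with 30-Day Mortality by Transplant Group (EVLP and Control) will be presented along with a two-sided 95% CI". No method is attached to either. Protocol 9.5.1 and 9.5.2 ask for a one-sided and a two-sided interval, again without a method. In 9.5.1 the wording is "A one-sided 95% CI will be calculated around the proportion", followed by the two-sided counterpart. Protocol 9.1 leaves the full methodology to the SAP, and SAP 4 names no interval method.

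A method appears only in the sample-size text (SAP 9, and likewise Protocol 9.2). There a one-sided 95% bound is computed "using the large sample normal approximation adjusted for a finite population of size 2057", with the conclusion that "66 subjects will be needed for the expected upper bound of the CI to not exceed a rate of 16" per cent, assuming a true PGD3 rate of 10%. For mortality, SAP 9 takes true rates of 3% to 4% and states that "the probability of observing at least one event will be approximately 87% to 93" per cent.

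The one-sided interval is no longer in SAP 6.1. The SAP Revisions table records its removal and gives a reason. Protocol 9.1 allows for this: "Any changes in the statistical methods described in this protocol that occur prior to database lock will be documented in the statistical analysis plan".

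**The concern.** The study tests no hypotheses, and SAP version 2.0 also dropped the intervals for the secondary and exploratory endpoints. The two intervals in 6.1 are therefore the only stated measure of uncertainty, and SAP 1 says the results may help to plan a pivotal study. The protocol hands the method to the SAP, and the SAP does not give it.

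The choice is not neutral at the expected counts: 66 × 0.10 = 6.6 PGD3 events and 66 × 0.03 to 0.04 = 2.0 to 2.6 deaths in the EVLP group. If the sizing approximation were taken over by default, coverage would fall below 95%. Most misses would be on the reassuring side, with an upper limit below the true rate, which is the wrong direction for a safety endpoint.

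A second worry is that the 16% in SAP 9 belongs to a one-sided bound that 6.1 no longer reports, so the SAP states no precision for the interval it will present.

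**Working it through.** **Inputs.** From SAP 9: n = 66 per group, planning rates of 10% (PGD3) and 3% to 4% (mortality), N = 2057. From SAP 6.1: two-sided 95%, so z = 1.96. The one-sided sizing calculation uses z = 1.645.

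**1. The plan's own figures.**

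- Upper bound = p + z·√(p(1−p)/n)·√((N−n)/(N−1)) = 0.10 + 1.645 × √(0.09/66) × √(1991/2056) = 0.1598. This is within 16%, and 66 is the smallest n that achieves it.
- Chance of at least one death: 1 − 0.97^66 = 86.6% and 1 − 0.96^66 = 93.2%, matching the stated 87% to 93%.

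SAP 9 is correct for what it states.

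**2. What if the normal approximation were used for analysis?** (An assumption; the SAP does not say so.) The interval is x/66 ± 1.96·√((x/66)(1−x/66)/66). Coverage is the binomial probability of those counts x whose interval contains the true rate.

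| True rate | Counts that cover | Normal approx. | Wilson | Clopper-Pearson | Normal upper limit below truth |
|---|---|---|---|---|---|
| 3% | 1 to 6 | 86.2% | 95.2% | 98.6% | 13.4% |
| 4% | 1 to 7 | 92.8% | 95.2% | 98.4% | 6.8% |
| 10% | 4 to 12 | 89.4% | 96.3% | 97.9% | 9.3% |

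Applying the finite population factor leaves the three normal-approximation coverages unchanged. At SAP 9's range for conventional transplants the effect is smaller: 93.1% at 16.8% and 93.7% at 30%.

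**3. Where the mortality shortfall comes from.** At 3% and 4% the upper limit falls below the truth only when no one dies: 0.97^66 = 13.4% and 0.96^66 = 6.8%. Given at least one death, coverage is 0.8624/0.8661 = 99.6% and 0.9276/0.9324 = 99.5%. The low coverage is thus almost wholly one outcome, 0/66, whose interval is 0% to 0%. One, two or three deaths give lower limits of −1.43%, −1.11% and −0.48%. Three or fewer deaths have probability 86% at a 3% rate and 73% at 4%. In most realisations, then, the output would be visibly unusable or would contain an impossible value.

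**4. Does the choice between sensible methods matter?**

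| Events/66 | Normal approx. | Wilson | Clopper-Pearson |
|---|---|---|---|
| 0 | 0% to 0% | 0% to 5.5% | 0% to 5.4% |
| 2 | −1.1% to 7.2% | 0.8% to 10.4% | 0.4% to 10.5% |
| 7 | 3.2% to 18.0% | 5.2% to 20.3% | 4.4% to 20.6% |

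The Wilson and Clopper-Pearson upper limits differ by about 0.1, 0.1 and 0.3 of a percentage point.

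**5. Precision of the two-sided interval.** By SAP 9's method: 0.10 + 1.96 × √(0.09/66) × √(1991/2056) = 17.1%. Averaged over a binomial count with n = 66 and rate 10%, the upper limit is 19.4% (Wilson) or 19.8% (Clopper-Pearson). Printing these would not alter n or any reported result.

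**The case for a change.** The best case for a change is that the SAP is the document assigned to settle the method, that a descriptive study leans harder on its intervals because there is no test behind them, and that one phrase would close the gap. An open method also lets the analyst choose after seeing the counts. The PGD3 interval is the awkward example: at 7/66 the normal approximation gives 3.2% to 18.0%, which looks plausible, yet its upper limit is 2.3 to 2.6 points lower than the alternatives. Unlike 0% to 0%, that would not announce itself.

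Much of this is true. The omission is a fact, and the PGD3 shortfall would be less visible than the mortality one. But it would arise only if an analyst took a large-sample sizing formula and applied it to about seven events, which no section instructs. Freedom to choose between the methods suited to small counts is worth about 0.3 of a point at the upper limit. The intervals meet no threshold: SAP 4 and 6.1 exclude testing, and the halting rules in Protocol 6.13.9 rest on a death count, an observed PGD3 rate and the Medical Monitor's judgement. The group proportions will be reported, so a reader who prefers another interval can compute it.

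On the second worry, SAP 9 records how n was set and is right for the one-sided bound it names. Dropping that bound from 6.1 was logged, explained and permitted, so restoring it would only reverse a legitimate choice.

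**Conclusion.** No change is needed. SAP 6.1 leaves out the interval method for both primary proportions, but this is missing detail rather than a flaw in the analysis. The 86% to 93% coverage is a property of a method the plan does not adopt for analysis, and in the mortality case it reflects the single outcome of no deaths. With either usual small-count method, coverage at the planning rates is 95.2% to 98.6%. The SAP 9 figures reproduce and can stand.

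This rests on three assumptions: that the sizing approximation is not carried into the analysis; that the true rates are near the planning rates; and that 66 subjects contribute to each proportion. The last two may shift a little. Missing 30-day vital status stays missing, which could lower the mortality denominator. Deaths before 72 hours and missing 72-hour scores count as PGD3, which could raise that count above 6.6 if the 10% planning rate does not already include them.

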6.2 Secondary Endpoints and Analyses

Secondary endpoints include the following:

- PGD Score (Grades 0-3) measured at 0, 24, 48 and 72 hours post-transplant
- Time to first extubation (hours)
- ICU LOS, measured as total number of days post-transplant in the ICU until first hospital discharge, inclusive of ICU readmissions during that hospitalization
- Hospital LOS, measured as total number of days in the hospital prior to discharge post-transplant
- TPT defined as the elapsed time between first allograft lung removal from cold storage time prior to transplant in the recipient and the donor aortic cross clamp time at procurement
- Assessment of the overall safety of TES lung transplants during subject's participation in the study, as reported through AEs.

The secondary endpoints of PGD score will be summarized by presenting the number of subjects and percentage for each category. All other secondary endpoints are continuous and will be presented using descriptive statistics by Transplant Group. Other supportive endpoints may be provided to supplement the secondary analyses. Analysis of the overall safety of TES lung transplants is detailed in Section 7.2.5.

Results may be displayed graphically. There will be no inferential testing conducted.

6.3 Exploratory Endpoints and Analyses

Other safety endpoints that will be analyzed include:

- Initial ICU PaO₂: Evaluated as first PaO₂ measured after ICU admission.
- FEV₁: Evaluated at time of discharge, 30 days, 90 days, 6 months and 1 year post-transplant. FEV₁ is measured as a percentage of predicted normal value. Oxygen Requirement at Rest: Evaluated at time of discharge, 30 days, 90 days, 6 months and 1 year post-transplant.
- Subject Survival: Evaluated at 90 days, 6 months and 1 year post-transplant. Measured as living or dead. If the subject expires within first year post-transplant, the date of death and primary cause of death will be collected.
- Graft Survival: Evaluated at 30 days, 90 days, 6 months and 1 year post-transplant. Measured as functioning or failed. If the graft fails within first year post-transplant, the date of graft failure will be collected.
- Primary Cause of Graft Failure: Evaluated at 30 days, 90 days, 6 months and 1 year posttransplant on all failed grafts.
- Bronchiolitis Obliterans Syndrome (BOS) Grade: Evaluated at 90 days 6 months and 1 year post-transplant.
- Number of Re-hospitalizations after Transplant: Evaluated at 6 months and 1 year post-transplant. Measured as total number of hospitalizations since initial discharge, the number of re-hospitalizations per subject, and whether the subject had a re-hospitalization related to transplant.
- Physical Capacity: Evaluated at 90 days, 6 months and 1 year post-transplant.
- Working for Income after Transplant: Evaluated at 90 days, 6 months and 1 year post-transplant.

Initial ICU PaO₂ and FEV₁ will be presented using descriptive statistics by Transplant Group. All other exploratory endpoints are categorical and will be summarized by presenting the number of subjects and percentage for each category. Other supportive endpoints may be included as needed.

Results may be displayed graphically. There will be no inferential testing conducted.

In addition, supplemental analyses comparing the EVLP group and the Control Group may be performed to provide context of results observed in this study.

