6.7 Primary Graft Dysfunction Score

The subject's PGD Score is to be determined by the Investigator at Baseline (Day 0) after transplantation and upon admission to the ICU, as well as 24, 48, and 72 hrs post-transplant. [Christie 2005]

PGD Score will be as graded using the parameters in Table 2, where the P/F ratio is PaO₂/FiO₂.

Table 2. Primary Graft Dysfunction Grading

Grade	P/F Ratio	Chest X-ray
0	>300	Normal
1	>300	Diffuse allograft infiltrates
2	200-300	Diffuse allograft infiltrates
3	<200	Diffuse allograft infiltrates

If the subject is on ECMO at any time point, the PGD grade is automatically assessed as “3”.

If the subject has been extubated prior to assessment, the presence or absence of radiographic infiltrates consistent with pulmonary edema will be reviewed and graded as follows for the PGD Grade:

- If subject is extubated AND the chest x-ray is “Absent” of infiltrates, then the PGD Score is 0.
- If subject is extubated AND the chest x-ray is “Present” of infiltrates, then the PGD Score is 1.

Graft survival will be evaluated by the Investigator (or his/her designee) at Day 30, Day 90, Month 6, Year 1 post-transplant, and premature termination (if applicable). Graft survival will be measured as functioning or failed. If the graft fails within first year post-transplant, the date of graft failure will be collected. The primary cause of graft failure will also be captured as one of the following:

- Primary Non-Function
- Acute Rejection
- Chronic Rejection
- or Other: (if Other, Specify)

After completion of the Analysis Phase, Graft Survival will be evaluated and collected annually by the Sponsor for the Long-term Follow-up Phase (Year 2, 3, 4, and 5).

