7.2.1.4 Lung Transplantation (Day 0)

Provided all recipient and lung Inclusion and Exclusion Criteria have been met, the Investigator or his/her designee will record the following at the time of admission to the ICU after lung transplantation:

- Hospital admission date
- Transplant date and time, including removal from cold storage time for each lung
- ICU admission time and date
- Initial PaO₂ and FiO₂ upon ICU admission
- PGD score (0 hrs)

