9.7 Exploratory Endpoints

Other safety endpoints that will be analyzed include:

- Initial ICU PaO₂: Evaluated as first PaO₂ measured after ICU admission.
- FEV₁: Evaluated at time of discharge, 30 days, 90 days, 6 months and 1 year post-transplant. FEV₁ is measured as a percentage of predicted normal value.

- Oxygen Requirement at Rest: Evaluated at time of discharge, 30 days, 90 days, 6 months and 1 year post-transplant.
- Subject Survival: Evaluated at 90 days, 6 months and 1 year post-transplant. Measured as living or dead. If the subject expires within first year post-transplant, the date of death and primary cause of death will be collected.
- Graft Survival: Evaluated at 30 days, 90 days, 6 months and 1 year post-transplant. Measured as functioning or failed. If the graft fails within first year post-transplant, the date of graft failure will be collected.
- Primary Cause of Graft Failure: Evaluated at 30 days, 90 days, 6 months and 1 year post-transplant on all failed grafts.
- Bronchiolitis Obliterans Syndrome (BOS) Grade: Evaluated at 90 days 6 months and 1 year post-transplant.
- Number of Re-hospitalizations after Transplant: Evaluated at 6 months and 1 year post-transplant. Measured as total number of hospitalizations since initial discharge.
- Physical Capacity: Evaluated at 90 days, 6 months and 1 year post-transplant.
- Working for Income after Transplant: Evaluated at 90 days, 6 months and 1 year post-transplant.

All exploratory endpoints will be presented using descriptive statistics along with two sided 95% CIs by Transplant Group. Other supportive endpoints may be included as needed.

Results may be displayed graphically. There will be no inferential testing conducted.

In addition, supplemental analyses comparing the EVLP group and the Control Group may be performed to provide context of results observed in this study (details will be described in the SAP).

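### Initial ICU PaO2 is summarised without the FiO2 recorded beside it, so the endpoint reflects the oxygen setting as well as lung function

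*SAP*

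**What the plan says.** SAP 6.3 defines the initial ICU PaO2 endpoint as the first PaO2 "measured after ICU admission" and gives its analysis in one sentence: "Initial ICU PaO₂ and FEV₁ will be presented using descriptive statistics by Transplant Group". Under SAP 4 that means the count, mean, SD, median, minimum and maximum. Protocol 2.3 and 9.7 carry the same PaO2-only definition; 9.7 reads "Initial ICU PaO₂: Evaluated as first PaO₂ measured after ICU admission".

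FiO2 is available. Protocol 7.2.1.4 says the investigator or designee "will record the following at the time of admission to the ICU after lung transplantation", and the list that follows includes "Initial PaO₂ and FiO₂ upon ICU admission". The Schedules of Events in both documents have one joint row for PaO2 and FiO2, marked at Day 0.

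Elsewhere the plan does relate oxygenation to FiO2. Protocol 6.7 grades PGD by Table 2, "where the P/F ratio is PaO₂/FiO₂". Protocol 5.2.3.1 sets a post-EVLP acceptance threshold on a PO2/FiO2 ratio. Protocol 3.1.1.2 sets FiO2 to 1.0 before each hourly perfusate gas sample. The recipient's initial ICU PaO2 is neither divided by FiO2 nor tied to a stated FiO2.

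**The concern.** Arterial PaO2 is the joint result of how well the lung transfers oxygen and how much oxygen is supplied. A table of raw PaO2 by group therefore mixes graft function with oxygen practice. Protocol 6 leaves post-transplant procedures to each center's standard of care, the groups are not randomised, and SAP 3.2.2 says blinding is not possible. Nothing in the design makes FiO2 comparable between EVLP and Control recipients at ICU admission.

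A graft that needs more oxygen can then show the same PaO2 as a better graft, or a higher one. What is at stake is how one exploratory table reads. That table is meant to give context for the EVLP results and to inform the control measures of later research (Protocol 2.3), and SAP 6.3 leaves room for supplemental comparisons between the groups. The primary endpoints and the sample size are not affected.

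**Working it through.** The plan states no figure for this endpoint, so there is none to reproduce. The check uses the protocol's own ratio and cut-offs.

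**Inputs**
- From Protocol 6.7: P/F = PaO2/FiO2. The Table 2 bands are >300 (Grade 0 or 1), 200-300 (Grade 2) and <200 (Grade 3). Grades 1 to 3 also require diffuse infiltrates on X-ray.
- Assumed: every PaO2, FiO2 and P/F value below. The documents give no distribution for any of them.

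**Step 1. One PaO2, several P/F values**

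| PaO2 (mmHg) | FiO2 | P/F | Table 2 band |
|---|---|---|---|
| 150 | 0.4 | 150/0.4 = 375 | >300 |
| 150 | 1.0 | 150/1.0 = 150 | <200 |
| 100 | 0.30 | 100/0.30 = 333 | >300 |
| 100 | 0.40 | 100/0.40 = 250 | 200-300 |
| 100 | 0.60 | 100/0.60 = 167 | <200 |

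The same endpoint value can lie in any of the three P/F bands.

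**Step 2. One P/F, several PaO2 values**

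With P/F fixed at 250, PaO2 = 250 × FiO2. This gives 75 mmHg at FiO2 0.30, 125 at 0.50 and 250 at 1.0. Raw PaO2 more than triples with no change in P/F.

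**Step 3. Can the order reverse?**

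- Graft A: P/F 350 at FiO2 0.4 gives PaO2 = 350 × 0.4 = 140 mmHg.
- Graft B: P/F 150 at FiO2 1.0 gives PaO2 = 150 × 1.0 = 150 mmHg.

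The graft with the lower P/F shows the higher raw PaO2, so reversal is arithmetically possible. Whether it would occur in the group summaries depends on FiO2 practice, which the documents do not describe.

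**Step 4. How large is the oxygen-setting share?**

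Since PaO2 = P/F × FiO2, log PaO2 = log P/F + log FiO2. Assume the two factors are independent and log-normal, so each log-variance is ln(1 + CV²). The share of log-PaO2 variance due to FiO2 is then

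ln(1 + CV_FiO2²) / [ln(1 + CV_FiO2²) + ln(1 + CV_P/F²)].

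For example, with CV_FiO2 = 0.3 and CV_P/F = 0.5: ln(1.09) / [ln(1.09) + ln(1.25)] = 0.0862/0.3093 = 28%.

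| CV of FiO2 | Share at P/F CV 50% | Share at P/F CV 30% |
|---|---|---|
| 10% | 4% | 10% |
| 20% | 15% | 31% |
| 30% | 28% | 50% |
| 40% | 40% | 63% |

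The share runs from 4% to 63% across these assumptions. The oxygen setting contributes in every case, but its weight relative to lung function cannot be fixed from the documents.

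**The case against.** The strongest reply is that FiO2-normalised oxygenation at ICU admission is already analysed at a higher rank. The PGD grade at 0 h is a secondary endpoint (SAP 6.2). It is determined on admission to the ICU (Protocol 6.7, SAP 6.1) and rests on P/F. This stands in large part, and it is why the point is minor. It does not dispose of the point. The grade is tabulated only in categories, ECMO forces Grade 3, and extubated subjects are graded on X-ray alone, so no continuous P/F summary is planned.

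Second, no hypotheses are tested and no formal comparison between groups is planned (SAP 4 and 9), so no decision rests on this variable. That also stands. It limits the consequence without making the raw summary easier to interpret.

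Third, SAP 6.3 allows further supportive endpoints and SAP 4 has subject data listed, so a P/F summary could be added. The plan permits it but does not specify it, and specifying it before database lock is better in an unblinded study.

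A reader might also infer more than the documents support:
- That the endpoint reflects the oxygen setting *as much as* lung function. Without an FiO2 distribution this cannot be shown.
- That one PaO2 value spans the whole PGD scale. It spans the P/F bands; the grade also depends on X-ray findings.
- That FiO2 practice will in fact differ between the groups. The documents say only that care follows center practice and that the study is unblinded.

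**Conclusion.** The point holds as a minor one. Raw initial ICU PaO2 is summarised by group although FiO2 is recorded at the same time, so the endpoint reflects the oxygen setting as well as lung function. Differing FiO2 practice could mask or reverse a descriptive difference. The examples show that this is possible, and they rest on assumed values. How much it would matter here is unknown, because the documents give no FiO2 distribution.

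The consequence is confined to one exploratory, descriptive table, and the 0 h PGD grade already gives a partial safeguard.

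**What to change.** In SAP 6.3, pre-specify initial ICU PaO2/FiO2 by Transplant Group, using the standard descriptive statistics of SAP 4. Report raw PaO2, as the protocol defines it, and FiO2 in adjacent rows. No confidence interval is needed: SAP version 2.0 removed intervals from the exploratory endpoints and gave its reason.

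Add a short rule for subjects on ECMO at the measurement, already extubated, or with FiO2 missing, for example whether they are left out of the P/F summary and counted separately. Protocol 6.7 already treats the first two outside the P/F bands when grading PGD.

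The cost is one variable derived from two collected fields, plus the handling rule. No new data are needed. Protocol 9.1 lets changes in statistical methods before database lock be documented in the SAP without a protocol amendment. Protocol 2.3 and 9.7 can be aligned if the protocol is next revised.
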